10.4 Trial listings - SAD

Note that the SAD listings will also include data from SAD sub-study: food interaction.

16.2.1 Discontinued subjects

- **Listing 16.2.1- 1 Discontinued subjects - SAD**
- **Listing 16.2.1- 2 Non-eligible subjects - SAD**
- **Listing 16.2.1- 3 Disposition - SAD (All subjects)**
- **Listing 16.2.1- 4 Subject visits - SAD (All subjects)**
- **Listing 16.2.1- 5 Subject elements - SAD (All subjects)**

16.2.2 Protocol deviations

- **Listing 16.2.2- 1 Protocol deviations - SAD (All subjects)**

16.2.3 Subjects excluded from the efficacy analysis

- **Listing 16.2.3- 1 Population definitions - SAD (All subjects)**

16.2.4 Demographic data

- **Listing 16.2.4- 1 Demography - SAD (All subjects)**
- **Listing 16.2.4- 2 Medical History - SAD (All subjects)**
- **Listing 16.2.4- 3 Prior and concomitant medications - SAD (All subjects)**
- **Listing 16.2.4- 4 Baseline events - SAD (All subjects)**

16.2.5 Compliance and/or Drug Concentration Data

- **Listing 16.2.5- 1 Plasma concentration data - SAD (All subjects)**
- **Listing 16.2.5- 2 Urine concentration data - SAD (All subjects)**
- **Listing 16.2.5- 3 Pharmacokinetic parameters - SAD (All subjects)**
- **Listing 16.2.5- 4 IMP administration - SAD (All subjects)**

16.2.6 Individual Efficacy Response Data

NA

16.2.7 Adverse event listings (each subject)

- **Listing 16.2.7- 1 Adverse events - SAD (All subjects)**
- **Listing 16.2.7- 2 Serious adverse events - SAD (All subjects)**

16.2.8 Listings of individual laboratory measurements subject

- **Listing 16.2.8- 1 Safety laboratory measurements: Clinical chemistry - SAD (All subjects)**
- **Listing 16.2.8- 2 Safety laboratory measurements: Haematology - SAD (All subjects)**
- **Listing 16.2.8- 3 Safety laboratory measurements: Coagulation - SAD (All subjects)**
- **Listing 16.2.8- 4 Other laboratory measurements - SAD (All subjects)**

Pregnancy test, Drug test, Alcohol screen

- **Listing 16.2.8- 5 Virology - SAD (All subjects)**

16.2.9 Listings of vital signs, ECG, physical examination data by subject

- **Listing 16.2.9- 1 Vital signs - SAD (All subjects)**
- **Listing 16.2.9- 2 ECG - SAD (All subjects)**
- **Listing 16.2.9- 3 Telemetry - SAD (All subjects)**
- **Listing 16.2.9- 4 Physical examinations - SAD (All subjects)**

16.2.10 Other data by participant

- **Listing 16.2.10- 1 Meals - SAD (All subjects)**
- **Listing 16.2.10- 2 Columbia-Suicide Severity Rating Scale (C-SSRS) - SAD (All subjects)**

11 DATA DISPLAY PLAN - MAD

Tables and figures will only be generated if sufficient data, with sufficient variability exist to justify specific output being produced. Unscheduled/extra visits will generally not be presented in tables and summary figures but will be included in listings.

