4.4 Subject replacement

The trial subjects withdrawn for medical/safety reasons will not be replaced.

Voluntary withdrawals can be replaced if they are not evaluable. See CTP for additional details.

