5.7 Handling of dropouts, missing data and outliers

Outliers will be included in summary tables and listings and will not be handled separately in any analyses. All collected data, even if not tabulated, will be listed. Generally, no imputation of data will be performed. However, when calculating statistics for PK plasma concentrations, concentrations under LLOQ will be replaced with LLOQ/2 if more than 50% of the values for a given time point are above LLOQ. For figures presenting individual PK concentrations, no imputation is performed for values under LLOQ. For imputation of PK plasma concentration below LLOQ with the purpose of calculating PK parameters, see Section 9.2.1.

Safety laboratory concentrations under LLOQ will be replaced with LLOQ/2 and concentrations over ULOQ will be replaced with ULOQ for the purpose of calculating descriptive statistics.

In case of missing start and stop times of AEs that cannot be investigated further, missing data will be imputed according to a worst-case scenario, i.e., start time will be imputed as the closest time point post first intake of IMP and end time as 23:59, resulting in the longest possible treatment emergent duration of the AE.

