9.1 Analysis of the primary endpoints

9.1.1 Adverse Events (AEs)

AEs and SAEs will be recorded from the time when informed consent is obtained until the Follow-up Visit. AEs that occur before first treatment with IMP (baseline symptoms) will be listed separately.

All AEs will be described in terms of the treatment at which they occurred. AEs will be summarised by System Organ Class (SOC) and Preferred Term (PT) using the Medical Dictionary for Regulatory Activities (MedDRA) vocabulary. The number of subjects reporting AEs, and the number of AEs reported will be presented. The events will be tabulated by SOC, PT and by severity and relationship to IMP. SAEs will be presented in the same tabulations.

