9.4 Description of trial population

9.4.1 Disposition

A subject disposition will be presented by part showing the number of screened subjects; the number of withdrawn subjects prior to dose, including the reason for withdrawal; the number of included subjects in each cohort; the number of withdrawn subjects, including the reason for withdrawal; the number of completed subjects; the number of subjects included in the analysis sets, and the number of subjects at each visit.

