11.2.2 Primary endpoints

11.2.2.1 Adverse events

Table AE 1 Overview of adverse events - MAD (Full analysis set)

| | IRL757 XX mg (N=9) | | IRL757 XX mg b.i.d. (N=9) | | IRL757 XX mg b.i.d. (N=9) | | All treated (N=XX) | | Placebo (N=XX) | | Total (N=XX) | |
|--|--------------------------|----|---------------------------------|----|---------------------------------|----|-----------------------|----|-------------------|----|-----------------|----|
| | n (%) | m | n (%) | m | n (%) | m | n (%) | m | n (%) | m | n (%) | m |
| Any AE | xx (xx%) | xx | xx (xx%) | xx | xx (xx%) | xx | xx (xx%) | xx | xx (xx%) | xx | xx (xx%) | xx |
| Any SAE | xx (xx%) | xx | xx (xx%) | xx | xx (xx%) | xx | xx (xx%) | xx | xx (xx%) | xx | xx (xx%) | xx |
| Any AE leading to withdrawal from trial | xx (xx%) | xx | xx (xx%) | xx | xx (xx%) | xx | xx (xx%) | xx | xx (xx%) | xx | xx (xx%) | xx |
| Any AE leading to death | xx (xx%) | xx | xx (xx%) | xx | xx (xx%) | xx | xx (xx%) | xx | xx (xx%) | xx | xx (xx%) | xx |
| Relationship to study treatment | | | | | | | | | | | | |
| Not related | xx (xx%) | xx | xx (xx%) | xx | xx (xx%) | xx | xx (xx%) | xx | xx (xx%) | xx | xx (xx%) | xx |
| Possible | xx (xx%) | xx | xx (xx%) | xx | xx (xx%) | xx | xx (xx%) | xx | xx (xx%) | xx | xx (xx%) | xx |
| Probable | xx (xx%) | xx | xx (xx%) | xx | xx (xx%) | xx | xx (xx%) | xx | xx (xx%) | xx | xx (xx%) | xx |
| Severity | | | | | | | | | | | | |
| Mild | xx (xx%) | xx | xx (xx%) | xx | xx (xx%) | xx | xx (xx%) | xx | xx (xx%) | xx | xx (xx%) | xx |
| Moderate | xx (xx%) | xx | xx (xx%) | xx | xx (xx%) | xx | xx (xx%) | xx | xx (xx%) | xx | xx (xx%) | xx |
| Severe | xx (xx%) | xx | xx (xx%) | xx | xx (xx%) | xx | xx (xx%) | xx | xx (xx%) | xx | xx (xx%) | xx |
| Life-Threatening | xx (xx%) | xx | xx (xx%) | xx | xx (xx%) | xx | xx (xx%) | xx | xx (xx%) | xx | xx (xx%) | xx |
| Death | xx (xx%) | xx | xx (xx%) | xx | xx (xx%) | xx | xx (xx%) | xx | xx (xx%) | xx | xx (xx%) | xx |

Data based on [ANALYSIS SET]. N: number of subjects in treatment group. Percentages are based on N. n: number of subjects. m: number of events. The following AEs are coded with multiple MedDRA terms and are represented as separate AEs in tables and listings: '[AE TERM 1]', '[AE TERM 2]', '[AE TERM 3]'. See listings for detailed information. SAS program: [PROGRAM NAME].sas.
Dataset version: ADXX YYYY-MM-DDTHH:MM:SS. Run by: [USERNAME] YYYY-MM-DDTHH:MM:SS. EDC data extracted: YYYY-MM-DDTHH:MM:SS.

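### An abnormal ECG, vital-sign or laboratory value seen only at an unscheduled assessment may be missing from the by-dose safety tables; the gap is widest for laboratory data

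*SAP*

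**What the plan says.** The sentence "Unscheduled/extra visits will generally not be presented in tables and summary figures but will be included in listings" opens both data display plans, SAP section 10 for SAD and section 11 for MAD. It is qualified by the word generally, and no exceptions are listed.

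The MAD shells show what the tables will contain. Tables EG 1 (ECG values), VS 1 (vital signs) and LB 1, 3 and 5 (laboratory values) give n, mean, SD, median, minimum, maximum and a 95% CI at each assessment time point. Tables EG 2 and LB 2, 4 and 6 give counts of interpretations at each time point. None has a row that takes each subject's records over the whole post-dose period. The corresponding SAD table shells are not shown in the available text.

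Three general rules in SAP 5.7 bear on this: "Generally, no imputation of data will be performed"; "Outliers will be included in summary tables and listings and will not be handled separately in any analyses"; and "All collected data, even if not tabulated, will be listed". On withdrawals, SAP 4.4 says "The trial subjects withdrawn for medical/safety reasons will not be replaced". SAP 9.4.1 tabulates "the number of withdrawn subjects, including the reason for withdrawal", and MAD Table AE 1 has a by-dose row for "Any AE leading to withdrawal from trial".

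**The concern.** ECG, vital signs and laboratory measurements are listed among the primary endpoints. A by-time-point table answers what the group looked like on a given day. It does not answer how many subjects had an abnormal result at any time after dosing, which is a natural question of a first-in-human safety table.

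The two questions give the same picture only if every abnormality falls on a scheduled assessment. Extra samples and repeat recordings exist because something may not fit the schedule, and those are the records the display rule generally leaves out. With six active subjects per SAD dose group and nine per MAD dose group, one omitted subject can be the whole signal at that dose. A reader comparing dose columns with placebo would have to rebuild the count from the listings.

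**Working it through.** The documents give no figure on this point to reproduce. The check compares the display rule with the shells and the visit schedules, followed by simple shares.

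**1. Path of an unscheduled value.** Under the rule in SAP 10 and 11 it generally enters no table. Under SAP 5.7 it is listed. If it is also reported as an AE, it is counted in the AE tables, where SAP 9.1.1 promises "The number of subjects reporting AEs, and the number of AEs reported will be presented" with no restriction by visit. In the available text, only the C-SSRS section (SAP 9.1.3) says outright that abnormal findings are treated as AEs.

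**2. How much of the post-dose period is scheduled** (Protocol Tables 3, 4 and 7 to 9).

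| Data | SAD, post-dose | MAD, post-dose |
|---|---|---|
| Laboratory | Day 3 (48 h) and follow-up | Days 2, 4, 7, 10, 12 and follow-up (Day 1 is pre-dose); coagulation only Days 7, 10 and follow-up |
| ECG | 1, 2, 3, 6, 12, 24, 48 h and follow-up | Day 1 at 1, 2, 3, 6, 12 h; once daily Days 2–10; Days 11, 12 and follow-up |
| Blood pressure, heart rate, respiratory rate | Seven times from 30 min to 24 h, Day 3 and follow-up | Serial on Day 1; once daily Days 2–10; Days 11, 12 and follow-up |

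- *SAD laboratory.* The first scheduled post-dose sample is at 48 h. With the synopsis's expected half-life of 2 to 7 h, that is 48/7 = 6.9 to 48/2 = 24 half-lives after the dose. Any laboratory value before then is unscheduled. The food sub-study follows the same pattern in each period (Protocol Table 5), with a further sample on the day before the second dose.
- *MAD laboratory.* The longest intervals during dosing are Day 4 to 7 and Day 7 to 10: 7 − 4 = 10 − 7 = 3 days. Follow-up is 5 to 10 days after the last dose on Day 10, so Day 15 to 20, which is 3 to 8 days after Day 12.
- *MAD ECG and vital signs.* No dosing day lacks a scheduled recording. What remains is time of day: on Days 2–10 the ECG is 2–4 h after the morning dose and vital signs within 1 h after it, while dosing is twice daily up to Day 9. A recording prompted by symptoms in the evening would be unscheduled.

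**3. Weight of one subject.** Allocation is 3:1, so 12 = 9 + 3 per MAD cohort and 8 = 6 + 2 per SAD cohort.

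- MAD dose group: 1/9 = 11.1%
- SAD dose group: 1/6 = 16.7%
- All MAD treated, three or two cohorts: 1/27 = 3.7% to 1/18 = 5.6%

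If exactly one subject in a MAD dose group has an abnormal interpretation, and only at an unscheduled sample (an assumption, for illustration), every time-point row for that parameter shows no abnormal result at that dose. An any-time row shows 1/9.

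**4. Consistency with the SAP's own aims.** SAP 5.7 keeps outliers in the summary tables, but an outlier from an unscheduled sample generally will not reach them. SAP section 6 says that the laboratory interpretation tables were added to give a better overview of those data, yet their by-time-point layout leaves out interpretations of extra samples.

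**The case against.** The strongest reply is that the information is not lost. All data are listed by subject, AEs are themselves a primary endpoint, Table AE 1 gives by-dose rates for withdrawals due to AEs, SAEs and severity, and disposition gives reasons for withdrawal. No hypothesis is tested on safety, and n is visible in each cell of the numeric tables. All of this stands, and it keeps the point small. It does not remove the point. Listings give no rate, an AE count gives no size of change, and the MAD disposition shell has a single total column rather than one per dose. The word generally allows exceptions but defines none.

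A reader might infer more: that the values which lead to a withdrawal drop out of the primary safety summaries, or that those summaries are biased towards no effect whenever an effect leads to stopping. The documents do not support this:

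- The rule excludes unscheduled visits, not values that lead to withdrawal. A decisive value at a scheduled time point is tabulated, and a scheduled value may well be what prompts the extra samples.
- The synopsis plans a follow-up visit for all subjects, and its laboratory, ECG and vital-sign results have their own scheduled place.
- Not replacing a subject withdrawn for safety does not remove that subject from the FAS.
- The available protocol text is the synopsis and schedules. It does not show whether early-withdrawal assessments count as unscheduled.
- In the SAD cohorts only one dose is given, so early stopping of treatment could arise only in the two-dose food sub-study.

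It is also tempting to size the problem by setting a group mean at a late time point beside a mean of each subject's highest value. That is not like with like, because maxima over repeated samples rise in unaffected subjects too.

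**Conclusion.** The point holds as a reporting gap. As written, the MAD ECG, vital-sign and laboratory tables may miss a post-dose abnormality seen only at an unscheduled or repeat assessment, and the exclusion sentence applies equally to SAD. The exposure is greatest for laboratory data in both parts and small for MAD ECG and vital signs.

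The size is one subject in nine or one in six per dose group for each such case. How often it would happen cannot be derived from the documents. The conclusion assumes that the general rule is followed without exception and that the abnormality is not also recorded at a scheduled time point. For SAD it further assumes tables laid out like the MAD ones. It does not establish a systematic bias. It is a cheap improvement.

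**What to change.** 1. In SAP sections 10 and 11, limit the sentence on unscheduled and extra visits to the by-time-point rows, and keep those rows as they are.
2. In Tables EG 2 and LB 2, 4 and 6, and the SAD equivalents, add a per-subject row for the worst post-dose interpretation at any time. Use all post-dose records, including unscheduled, repeat and early-withdrawal assessments. The denominator is every FAS subject with a post-dose value. State the order of the categories; SAP 9.1.4 names them for ECG, while the laboratory shell has placeholders.
3. In Tables EG 1, VS 1 and LB 1, 3 and 5, and the SAD equivalents, add rows for the per-subject post-dose maximum and minimum. Both are needed because worst has no single direction for parameters such as blood pressure, heart rate or potassium.
4. In the food sub-study, form these rows within each treatment period, as SAP 5.4 does for baseline. State how early-withdrawal assessments map to time points.
5. Footnote that subjects with more repeat assessments have more chances of an extreme value, and read the rows against the pooled placebo column (6 or 9 subjects for two or three MAD cohorts; 5 × 2 = 10 in SAD).

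The cost is SAP wording and a few derived rows from data already collected. Nothing changes in the visit schedule. The one real drawback is the uneven number of assessments, which the footnote and the placebo column make visible but do not remove.

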11.2 Trial tables - MAD

11.2.1 Demographic data

Table DM 1 Baseline characteristics and demographics - MAD (Full analysis set)

| Assessment (unit) | | IRL757 XX mg b.i.d. (N=9) | IRL757 XX mg b.i.d. (N=9) | IRL757 XX mg b.i.d. (N=9) | All treated (N=XX) | Placebo (N=XX) | Total (N=XX) |
|--------------------------------------|----------------------------------|---------------------------------|---------------------------------|---------------------------------|-----------------------|--------------------|--------------------|
| Age (years) | n | x | x | x | x | x | x |
| | Mean (SD) | xx.x (xx.x) | xx.x (xx.x) | xx.x (xx.x) | xx.x (xx.x) | xx.x (xx.x) | xx.x (xx.x) |
| | Median (Min, Max) | xx.x (xx, xx) | xx.x (xx, xx) | xx.x (xx, xx) | xx.x (xx, xx) | xx.x (xx, xx) | xx.x (xx, xx) |
| Height (cm) | n | x | x | x | x | x | x |
| | Mean (SD) | xxx.x (xx.x) | xxx.x (xx.x) | xxx.x (xx.x) | xxx.x (xx.x) | xxx.x (xx.x) | xxx.x (xx.x) |
| | Median (Min, Max) | xxx.x (xxx, xxx) | xxx.x (xxx, xxx) | xxx.x (xxx, xxx) | xxx.x (xxx, xxx) | xxx.x (xxx, xxx) | xxx.x (xxx, xxx) |
| Weight (kg) | n | x | x | x | x | x | x |
| | Mean (SD) | xx.xx (xx.xx) | xx.xx (xx.xx) | xx.xx (xx.xx) | xx.xx (xx.xx) | xx.xx (xx.xx) | xx.xx (xx.xx) |
| | Median (Min, Max) | xx.xx (xx.x, xx.x) | xx.xx (xx.x, xx.x) | xx.xx (xx.x, xx.x) | xx.xx (xx.x, xx.x) | xx.xx (xx.x, xx.x) | xx.xx (xx.x, xx.x) |
| Body Mass Index (kg/m ²) | n | x | x | x | x | X | X |
| | Mean (SD) | xx.xx (xx.xx) | xx.xx (xx.xx) | xx.xx (xx.xx) | xx.xx (xx.xx) | xx.xx (xx.xx) | xx.xx (xx.xx) |
| | Median (Min, Max) | xx.xx (xx.x, xx.x) | xx.xx (xx.x, xx.x) | xx.xx (xx.x, xx.x) | xx.xx (xx.x, xx.x) | xx.xx (xx.x, xx.x) | xx.xx (xx.x, xx.x) |
| Sex | Female | xx (xx%) | xx (xx%) | xx (xx%) | xx (xx%) | xx (xx%) | xx (xx%) |
| | Male | xx (xx%) | xx (xx%) | xx (xx%) | xx (xx%) | xx (xx%) | xx (xx%) |
| Ethnicity | Hispanic or latino | xx (xx%) | xx (xx%) | xx (xx%) | xx (xx%) | xx (xx%) | xx (xx%) |
| | Not hispanic or latino | xx (xx%) | xx (xx%) | xx (xx%) | xx (xx%) | xx (xx%) | xx (xx%) |
| | Not reported | xx (xx%) | xx (xx%) | xx (xx%) | xx (xx%) | xx (xx%) | xx (xx%) |
| | Unknown | xx (xx%) | xx (xx%) | xx (xx%) | xx (xx%) | xx (xx%) | xx (xx%) |
| Race | American Indian or Alaska Native | xx (xx%) | xx (xx%) | xx (xx%) | xx (xx%) | xx (xx%) | xx (xx%) |
| | Asian | xx (xx%) | xx (xx%) | xx (xx%) | xx (xx%) | xx (xx%) | xx (xx%) |
| | Black or African American | xx (xx%) | xx (xx%) | xx (xx%) | xx (xx%) | xx (xx%) | xx (xx%) |

| Assessment (unit) | IRL757 XX mg b.i.d. (N=9) | IRL757 XX mg b.i.d. (N=9) | IRL757 XX mg b.i.d. (N=9) | All treated (N=XX) | Placebo (N=XX) | Total (N=XX) |
|---|---------------------------------|---------------------------------|---------------------------------|-----------------------|-------------------|-----------------|
| Native Hawaiian or Other Pacific Islander | xx (xx%) | xx (xx%) | xx (xx%) | xx (xx%) | xx (xx%) | xx (xx%) |
| White | xx (xx%) | xx (xx%) | xx (xx%) | xx (xx%) | xx (xx%) | xx (xx%) |

Data based on [ANALYSIS SET]. N: number of subjects in treatment group. Mean values and percentages are based on n. n: Number of observations.
SD: Standard deviation. SAS program: [PROGRAM NAME].sas.
Dataset version: ADXX YYYY-MM-DDTHH:MM:SS. Run by: [USERNAME] YYYY-MM-DDTHH:MM:SS. EDC data extracted: YYYY-MM-DDTHH:MM:SS.

Table DS 1 Subject disposition - MAD (All subjects)

| | Total (N=XXX) |
|--|------------------|
| Screened subjects | xxx |
| Withdrawn prior to dose | xxx |
| Reason for withdrawal prior to dose | |
| --- Reason 1 | xxx |
| --- Reason 2 | xxx |
| --- ... | xxx |
| Subjects included in MAD part of trial | xxx |
| Allocated to arm | |
| --- IRL757 XX mg b.i.d. | xxx |
| --- IRL757 XX mg b.i.d. | xxx |
| --- IRL757 XX mg b.i.d. | xxx |
| --- Placebo ¹ | xxx |
| Withdrawn subjects | |
| --- Reason 1 | xxx |
| --- Reason 2 | xxx |
| --- ... | xxx |
| Completed subjects | xxx |
| Included in Full analysis set | xxx |
| Included in Pharmacokinetic analysis set | xxx |
| Subjects at each visit | |
| --- Visit 1 - Screening | xxx |
| --- Visit 2 - In-clinic | xxx |
| --- Visit 3 - Ambulatory | xxx |
| --- Visit 4 - Follow-up | xxx |

Data based on All subjects. ¹The data for subjects receiving placebo is presented pooled across groups. SAS program: [PROGRAM NAME].sas.
Dataset version: ADXX YYYY-MM-DDTHH:MM:SS. Run by: [USERNAME] YYYY-MM-DDTHH:MM:SS. EDC data extracted: YYYY-MM-DDTHH:MM:SS.

Table MH 1 Medical history events by system organ class and preferred term - MAD (Full analysis set)

| System organ class Preferred term | IRL757 XX mg b.i.d. (N=9) | | IRL757 XX mg b.i.d. (N=9) | | IRL757 XX mg b.i.d. (N=9) | | All treated (N=XX) | | Placebo (N=XX) | | Total (N=XX) | |
|--------------------------------------|---------------------------------|-----------|---------------------------------|-----------|---------------------------------|-----------|-----------------------|-----------|-------------------|-----------|-----------------|-----------|
| | n (%) | m | n (%) | m | n (%) | m | n (%) | m | n (%) | m | n (%) | m |
| Total | xx (xx%) | xx | xx (xx%) | xx | xx (xx%) | xx | xx (xx%) | xx | xx (xx%) | xx | xx (xx%) | xx |
| [SOC 1] | xx (xx%) | xx | xx (xx%) | xx | xx (xx%) | xx | xx (xx%) | xx | xx (xx%) | xx | xx (xx%) | xx |
| [SOC 1 PT 1] | xx (xx%) | xx | xx (xx%) | xx | xx (xx%) | xx | xx (xx%) | xx | xx (xx%) | xx | xx (xx%) | xx |
| [SOC 1 PT 2] | xx (xx%) | xx | xx (xx%) | xx | xx (xx%) | xx | xx (xx%) | xx | xx (xx%) | xx | xx (xx%) | xx |
| [SOC 1 PT ...] | xx (xx%) | xx | xx (xx%) | xx | xx (xx%) | xx | xx (xx%) | xx | xx (xx%) | xx | xx (xx%) | xx |
| [SOC 2] | xx (xx%) | xx | xx (xx%) | xx | xx (xx%) | xx | xx (xx%) | xx | xx (xx%) | xx | xx (xx%) | xx |
| [SOC 2 PT 1] | xx (xx%) | xx | xx (xx%) | xx | xx (xx%) | xx | xx (xx%) | xx | xx (xx%) | xx | xx (xx%) | xx |
| [SOC 2 PT 2] | xx (xx%) | xx | xx (xx%) | xx | xx (xx%) | xx | xx (xx%) | xx | xx (xx%) | xx | xx (xx%) | xx |
| [SOC 2 PT ...] | xx (xx%) | xx | xx (xx%) | xx | xx (xx%) | xx | xx (xx%) | xx | xx (xx%) | xx | xx (xx%) | xx |
| [SOC ...] | xx (xx%) | xx | xx (xx%) | xx | xx (xx%) | xx | xx (xx%) | xx | xx (xx%) | xx | xx (xx%) | xx |
| [SOC ... PT 1] | xx (xx%) | xx | xx (xx%) | xx | xx (xx%) | xx | xx (xx%) | xx | xx (xx%) | xx | xx (xx%) | xx |
| [SOC ... PT 2] | xx (xx%) | xx | xx (xx%) | xx | xx (xx%) | xx | xx (xx%) | xx | xx (xx%) | xx | xx (xx%) | xx |
| [SOC ... PT ...] | xx (xx%) | xx | xx (xx%) | xx | xx (xx%) | xx | xx (xx%) | xx | xx (xx%) | xx | xx (xx%) | xx |

Data based on [ANALYSIS SET]. N: number of subjects in treatment group. Percentages are based on N. n: number of subjects. m: number of events. The following events are coded with multiple terms and are represented as separate events in tables and listings: '[MH TERM 1]', '[MH TERM 2]'. See listings for detailed information. SAS program: [PROGRAM NAME].sas.
Dataset version: ADXX YYYY-MM-DDTHH:MM:SS. Run by: [USERNAME] YYYY-MM-DDTHH:MM:SS. EDC data extracted: YYYY-MM-DDTHH:MM:SS.

Table CM 1 Prior medications by ATC classification and active ingredients - MAD (Full analysis set)

| | IRL757 XX mg b.i.d. (N=9) | | IRL757 XX mg b.i.d. (N=9) | | IRL757 XX mg b.i.d. (N=9) | | All treated (N=XX) | | Placebo (N=XX) | | Total (N=XX) | |
|---|---------------------------------|-----------|---------------------------------|-----------|---------------------------------|-----------|-----------------------|-----------|-------------------|-----------|-----------------|-----------|
| ATC classification | | | | | | | | | | | | |
| Active Ingredients | n (%) | m | n (%) | m | n (%) | m | n (%) | m | n (%) | n (%) | n (%) | m |
| Total | xx (xx%) | xx | xx (xx%) | xx | xx (xx%) | xx | xx (xx%) | xx | xx (xx%) | xx | xx (xx%) | xx |
| [ATC classification 1] | xx (xx%) | xx | xx (xx%) | xx | xx (xx%) | xx | xx (xx%) | xx | xx (xx%) | xx | xx (xx%) | xx |
| [ATC classification 1 Active Ingredients 1] | xx (xx%) | xx | xx (xx%) | xx | xx (xx%) | xx | xx (xx%) | xx | xx (xx%) | xx | xx (xx%) | xx |
| [ATC classification 1 Active Ingredients 2] | xx (xx%) | xx | xx (xx%) | xx | xx (xx%) | xx | xx (xx%) | xx | xx (xx%) | xx | xx (xx%) | xx |
| [ATC classification 1 Active Ingredients ...] | xx (xx%) | xx | xx (xx%) | xx | xx (xx%) | xx | xx (xx%) | xx | xx (xx%) | xx | xx (xx%) | xx |
| [ATC classification 2] | xx (xx%) | xx | xx (xx%) | xx | xx (xx%) | xx | xx (xx%) | xx | xx (xx%) | xx | xx (xx%) | xx |
| [ATC classification 2 Active Ingredients 1] | xx (xx%) | xx | xx (xx%) | xx | xx (xx%) | xx | xx (xx%) | xx | xx (xx%) | xx | xx (xx%) | xx |
| [ATC classification 2 Active Ingredients 2] | xx (xx%) | xx | xx (xx%) | xx | xx (xx%) | xx | xx (xx%) | xx | xx (xx%) | xx | xx (xx%) | xx |
| [ATC classification 2 Active Ingredients ...] | xx (xx%) | xx | xx (xx%) | xx | xx (xx%) | xx | xx (xx%) | xx | xx (xx%) | xx | xx (xx%) | xx |
| [ATC classification ...] | xx (xx%) | xx | xx (xx%) | xx | xx (xx%) | xx | xx (xx%) | xx | xx (xx%) | xx | xx (xx%) | xx |
| [ATC classification ... Active Ingredients 1] | xx (xx%) | xx | xx (xx%) | xx | xx (xx%) | xx | xx (xx%) | xx | xx (xx%) | xx | xx (xx%) | xx |
| [ATC classification ... Active Ingredients 2] | xx (xx%) | xx | xx (xx%) | xx | xx (xx%) | xx | xx (xx%) | xx | xx (xx%) | xx | xx (xx%) | xx |
| [ATC classification ... Active Ingredients ...] | xx (xx%) | xx | xx (xx%) | xx | xx (xx%) | xx | xx (xx%) | xx | xx (xx%) | xx | xx (xx%) | xx |

Data based on [ANALYSIS SET]. N: number of subjects in treatment group. Percentages are based on N. n: number of subjects. m: number of events. The following records are coded with multiple terms and are represented as separate events in tables and listings: '[CM TERM 1], [CM TERM 2]'. See listings for detailed information. SAS program: [PROGRAM NAME].sas.
Dataset version: ADXX YYYY-MM-DDTHH:MM:SS. Run by: [USERNAME] YYYY-MM-DDTHH:MM:SS. EDC data extracted: YYYY-MM-DDTHH:MM:SS.

Table CM 2 Concomitant medications by ATC classification and active ingredients - MAD (Full analysis set)

| | IRL757 XX mg b.i.d. (N=9) | | IRL757 XX mg b.i.d. (N=9) | | IRL757 XX mg b.i.d. (N=9) | | All treated (N=XX) | | Placebo (N=XX) | | Total (N=XX) | |
|---|---------------------------------|-----------|---------------------------------|-----------|---------------------------------|-----------|-----------------------|-----------|-------------------|-----------|-----------------|-----------|
| ATC classification | | | | | | | | | | | | |
| Active Ingredients | n (%) | m | n (%) | m | n (%) | m | n (%) | m | n (%) | m | n (%) | m |
| Total | xx (xx%) | xx | xx (xx%) | xx | xx (xx%) | xx | xx (xx%) | xx | xx (xx%) | xx | xx (xx%) | xx |
| [ATC classification 1] | xx (xx%) | xx | xx (xx%) | xx | xx (xx%) | xx | xx (xx%) | xx | xx (xx%) | xx | xx (xx%) | xx |
| [ATC classification 1 Active Ingredients 1] | xx (xx%) | xx | xx (xx%) | xx | xx (xx%) | xx | xx (xx%) | xx | xx (xx%) | xx | xx (xx%) | xx |
| [ATC classification 1 Active Ingredients 2] | xx (xx%) | xx | xx (xx%) | xx | xx (xx%) | xx | xx (xx%) | xx | xx (xx%) | xx | xx (xx%) | xx |
| [ATC classification 1 Active Ingredients ...] | xx (xx%) | xx | xx (xx%) | xx | xx (xx%) | xx | xx (xx%) | xx | xx (xx%) | xx | xx (xx%) | xx |
| [ATC classification 2] | xx (xx%) | xx | xx (xx%) | xx | xx (xx%) | xx | xx (xx%) | xx | xx (xx%) | xx | xx (xx%) | xx |
| [ATC classification 2 Active Ingredients 1] | xx (xx%) | xx | xx (xx%) | xx | xx (xx%) | xx | xx (xx%) | xx | xx (xx%) | xx | xx (xx%) | xx |
| [ATC classification 2 Active Ingredients 2] | xx (xx%) | xx | xx (xx%) | xx | xx (xx%) | xx | xx (xx%) | xx | xx (xx%) | xx | xx (xx%) | xx |
| [ATC classification 2 Active Ingredients ...] | xx (xx%) | xx | xx (xx%) | xx | xx (xx%) | xx | xx (xx%) | xx | xx (xx%) | xx | xx (xx%) | xx |
| [ATC classification ...] | xx (xx%) | xx | xx (xx%) | xx | xx (xx%) | xx | xx (xx%) | xx | xx (xx%) | xx | xx (xx%) | xx |
| [ATC classification ... Active Ingredients 1] | xx (xx%) | xx | xx (xx%) | xx | xx (xx%) | xx | xx (xx%) | xx | xx (xx%) | xx | xx (xx%) | xx |
| [ATC classification ... Active Ingredients 2] | xx (xx%) | xx | xx (xx%) | xx | xx (xx%) | xx | xx (xx%) | xx | xx (xx%) | xx | xx (xx%) | xx |
| [ATC classification ... Active Ingredients ...] | xx (xx%) | xx | xx (xx%) | xx | xx (xx%) | xx | xx (xx%) | xx | xx (xx%) | xx | xx (xx%) | xx |

Data based on [ANALYSIS SET]. N: number of subjects in treatment group. Percentages are based on N. n: number of subjects. m: number of events. The following records are coded with multiple terms and are represented as separate events in tables and listings: '[CM TERM 1], [CM TERM 2]'. See listings for detailed information. SAS program: [PROGRAM NAME].sas.
Dataset version: ADXX YYYY-MM-DDTHH:MM:SS. Run by: [USERNAME] YYYY-MM-DDTHH:MM:SS. EDC data extracted: YYYY-MM-DDTHH:MM:SS.

